The safety objective of this study is to collect additional safety data for ACS patients who undergo the LDL-apheresis post-PCI procedure and the use of maximum dose of statin drugs.

The primary effectiveness objective of this study is to compare the total atheroma volume within a ≥ 20 mm long segment of the target coronary artery in ACS patients with an uncomplicated PCI randomly assigned to LDL-apheresis with 40-80mg daily of Atorvastatin or equivalent (ILLT group) or 40-80mg daily of Atorvastatin or equivalent only (SMT group). The specific hypothesis being tested is: ILLT is superior to SMT in reducing the total atheroma volume at 90 days IVUS-VH follow up.

The secondary effectiveness objectives of this study will be: (1) to compare %NC component of atheroma within a ≥ 20 mm long segment of the target coronary artery; (2) to compare the EPC-CFU/ml of peripheral blood in the two treatment groups; and (3) to compare MACE, associated with the two treatment groups at 90 days and at 6 month follow-up.

Rationale for study effectiveness objectives: The rationale for the study effectiveness objectives includes the observation of increased recurrent CV events in ACS patients early (three months) post-index event, despite intensive statin pharmacotherapy, due to progression and rupture of non-critical coronary lesions. Aggressive LDL lowering using LDL-apheresis (ILLT) as proposed in this study will test a novel strategy of non-critical coronary atheroma regression at 90 days, and hence reduce early (12-week) MACE events in ACS patients, sustained at end of study (at least six months follow-up). We also propose to test whether EPC mobilization with aggressive LDL lowering correlates with coronary atheroma regression, change in atheroma composition (%NC), and MACE events. We acknowledge that the scope of this study does not test the mechanism of EPC targeting to site of coronary VP and its endothelialization, however, it would provide for the first time important initial evidence which could be tested in future dedicated studies.

We expect to demonstrate a significant reduction in atheroma volume at 90 days by IVUS-VH (primary endpoint) because this study will have the most aggressive LDL lowering strategy in ACS patients ever tested in non-FH ACS patients. The 12-week time period is also the time point when early post-ACS CV events begin to increase, as seen in the PROVE IT-TIMI 22 trial⁹. Currently there are two clinical studies that have evaluated early (≤ 12 week) IVUS derived coronary atheroma regression and have demonstrated significant regression from baseline with pre-beta HDL²¹ and ApoA-1

Milano²⁰ infusions. The change in atheroma volume in the control arm was 2.8mm³ (increase) and that in the treatment arms were -12.18mm³ and -14.1mm³ with pre-beta HDL and ApoA-1 Milano therapies respectively. We also expect a robust response to ILLT with LDL-apheresis at 90 days. Our estimates of effect are much more conservative and have been described in detail in Section 4(g) under "Biostatistical Considerations".

4(b) Study Outcome Measures

The primary safety outcome measures will be the total number of and percentage of patients with major peri-PCI procedure adverse events, such as hypotension, angina, myocardial ischemia, myocardial infarction (if the patient is determined to have had unstable angina rather than non-ST-elevation MI at admission), cerebrovascular event (CVA), vermicular tachycardia, bleeding (at the PCI access and apheresis cannulation sites in the apheresis patients and at the PCI access site in the non-apheresis control patients), and death. The peri-PCI procedure is defined as encompassing the time of the PCI procedure and the time of the subsequent LDL-apheresis procedure for ILLT group vs. the time of the PCI procedure for SMT group. All LDL-apheresis-related adverse events in the ILLT group, including any minor expected events, will be recorded.

The secondary safety outcome measures will be the total number of and percentage of patients with statin-related abnormal liver function test events and statin-related muscle injury events, which could occur due to the maximum dose of statin drugs being given to both the ILLT group and SMT group patients. The statin-related muscle injury is defined as a muscle injury which cannot be attributed to a non-statin cause and which is evidenced by symptoms (muscle soreness, pain, or tenderness) and/or lab tests such as serum total creatine phosphokinase (CPK), CPK-MM, or myoglobin.

The primary effectiveness outcome measure will be the change in the total atheroma volume within a ≥ 20 mm long segment of the target coronary artery from baseline to 90 days post-PCI. The measurement will be done via IVUS-VH at both centers of investigation.

[figure not shown]
The secondary effectiveness outcome measures will include the %NC component of atheroma, EPC-CFU/ml of peripheral blood, and major adverse cardiovascular endpoints (MACE) including death, myocardial infarction, coronary revascularization, and stroke during the follow-up periods. The cell culture assay and quantification of circulating EPC-CFU will be done for patients recruited at the Dallas VA center. The major adverse CV events will be collected via both clinical visit and searches of the Austin database for VA hospital utilization by Hines staff. Approvals for using the patients' Social Security numbers for data searching will be obtained.

4(c) Study Design and Procedures

The proposed study is a multi-center, randomized controlled study comparing atheroma volume, %NC component, and peripherally circulating EPC-CFU/ml of blood in ILLT vs. SMT groups of ACS patients undergoing PCI (**Figure 7**). All patients will sign an informed consent during the index hospital admission for ACS but prior to any study-

related procedure. The protocol will be approved by each site's institutional review board.

Figure 7: Study design overview for primary endpoint:

4(c)(i). Subject Screening Criteria (Figure 7, green arrow): Patients presenting with an ACS, LDL ≥ 70 mg/dl on Atorvastatin ≤ 80 mg or equivalent dose of another statin, normal liver function test (LFT) and referred for non-emergent cardiac catheterization (the procedure is not required to be performed within 3 hours after patient presentation) will be screened and consented during the index hospital admission for ACS. Patients on ACE inhibitors will either have it discontinued or switched to an angiotensin receptor blocking agent (ARB). All screen eligible patients will be subsequently asked to sign an IRB-approved informed consent form prior to clinically indicated PCI or any subsequent study related tests.

ACS is defined as chest discomfort lasting at least 10 min within the last 24h, new ≥ 1 mm ST-wave or dynamic T-wave changes in at least two contiguous EKG leads but without significant ST elevation, and/or troponin I or T levels above the 99th percentile. Abnormal LFT is defined as any liver transaminases (ALT or AST) ≥ 3 times the upper limit of the normal laboratory reference. Atorvastatin 40-80mg will be considered equivalent to 20-40mg of Rosuvastatin. Patients on Simvastatin at the time of enrollment will be switched to Atorvastatin 40-80 mg or Rosuvastatin 20-40 mg.

After PCI of the target or culprit coronary artery (as determined by the operator) and IVUS-VH analysis of a ≥ 20 mm segment of the target coronary artery are performed during the index hospitalization for the qualifying ACS event, the patients will be randomized to ILLT or SMT if they meet all inclusion and exclusion criteria (**Figure 7, blue arrow**). PCI will be performed using standard technique at the discretion of the operator. 40-80mg daily Atorvastatin or equivalent treatments (ILLT or SMT) will be initiated within 24 hours after randomization. Patients randomized to the ILLT arm will undergo LDL-apheresis within 36 hours after presentation unless the 36-hour window is mandatory for those who were on ACE inhibitors to allow for the complete washout of ACE inhibitors. Adjunctive anti-platelet and anti-thrombin therapies will be at the discretion of the primary operator and clinical team. Refer to **Figure 8** for all study timelines.

4(c)(ii). Inclusion Criteria:

- (1). Willing and able to provide informed consent (including HIPAA)
- (2). Age > 30 years

- (3). Presenting with acute coronary syndrome (ACS), manifested as unstable angina or non-ST-elevation myocardial infarction
- (4). Referred for clinically indicated, non-emergent (the procedure is not required to be performed within 3 hours after patient presentation) coronary angiography and PCI with IVUS-VH of target coronary artery for ACS
- (5). Successful placement of two large-bore IV cannulas in bilateral upper extremities
- (6). Fasting (≥ 12 hrs) LDL ≥ 70 mg/dl while on ≤ 80 mg Atorvastatin or equivalent dose of other statin, performed at time of admission

4(c)(iii). Exclusion Criteria:

- (1). Known allergy to aspirin, statins, or iodinated contrast
- (2). Positive pregnancy test, planning to become pregnant, or breast-feeding
- (3). Coexisting conditions that limit life expectancy to less than six months or affect patient compliance
- (4). Uncontrolled fasting (≥ 12 hrs) triglyceride levels (≥ 500 mg/dl)
- (5). Already participating in an investigational device or drug study
- (6). History of heparin induced thrombocytopenia (HIT)
- (7). Persons with estimated GFR less than 45 ml/min
- (8). ST-elevation myocardial infarction at admission
- (9). Abnormal liver function test (LFT) at time of admission, with abnormal LFT defined as any liver transaminases (ALT or AST) ≥ 3 times the upper limit of the normal laboratory reference
- (10). Pre-PCI or post-PCI left ventricular ejection fraction $< 25\%$ by echo or cardiac catheterization done after admission
- (11). Pre-PCI, intra-PCI, or post-PCI hemodynamic instability with hypotension
- (12). Pre-PCI, intra-PCI, or post-PCI cardiac arrest
- (13). Pre-PCI or post-PCI acute heart failure with or without pulmonary edema
- (14). Intra-PCI or post-PCI sustained ventricular tachycardia
- (15). Complicated PCI, defined as PCI with any of the vascular access complications (large hematoma with lump > 5 cm or requiring medical treatment; AV fistula; pseudo aneurysm requiring treatment; retroperitoneal bleeding), or PCI with any of the procedural complications (abrupt vessel closure; no-reflow phenomenon; new angiographic thrombus; new major dissection with reduced flow; catheter-related thrombus), or PCI requiring further medical treatments (urgent CABG; endotracheal intubation; unplanned in-aortic balloon pump; LVAD; covered stent; unplanned temporary pacemaker wire; administration of inotropes; CPR) , or PCI resulting in clinical events (death; stroke; myocardial infarction; stent thrombosis) during or within 24 hours after the index PCI
- (16). Post-PCI ongoing chest pain
- (17). Post-PCI severe groin pain and hematoma > 5 cm in diameter

- (18). Persons whose hemoglobin is less than 9 grams following the index PCI/IVUS procedure, or who experience a drop in hemoglobin of greater than or equal to 2 grams following the procedure
- (19). Not able to comply with study protocol as determined by the investigators

4(c)(iv). Baseline Data Collection: A complete history and physical, 12-lead electrocardiogram, lipid panel, basic metabolic panel (BMP) with LFT, complete blood count, and complete cardiac catheterization, PCI, IVUS-VH and adjunctive pharmacotherapy data will be collected on all eligible patients apart from demographic and contact information.

4(c)(v). Stratification and Randomization: Prior to randomizing a patient, all screening and baseline assessments must be completed and the patient determined to be eligible for inclusion in the study. Eligible patients will be randomized to one of two treatment groups (ILLT or SMT) following an uncomplicated index PCI. 40-80mg daily Atorvastatin or equivalent statin medication treatment (ILLT or SMT) will be initiated within 24h after randomization and LDL-apheresis for ILLT group will be initiated within 36 hours of hospital admission unless the 36-hour window is mandatory for those who were on ACE inhibitors to allow for the complete washout of ACE inhibitors. Refer to **Figure 8** for all study timelines. Screening and randomization will be performed by a study coordinator, and LDL-apheresis will be conducted by a contracted specialized apheresis nurse.

4(c)(v)(1). Randomization Methods: The randomization scheme and associated codes will be developed by the Cooperative Studies Program Coordinating Center (CSPCC). Permuted block randomization with random block sizes will be employed to assign patients to either ILLT or SMT in a 1:1 ratio. The randomization will be stratified by investigation sites only.

4(c)(v)(2). Randomization and Blinding Procedures: Following an uncomplicated PCI procedure, patients who are eligible and willing to participate in the study will be randomly assigned to either the ILLT or SMT arm using an automated telephone-based randomization system. A touch-tone phone is necessary to use this Voice Information System (VIS) to randomize eligible subjects. CSPCC will assign each site a unique 6-digit PIN that the unblinded staff can use to access the VIS system and randomize a subject (or add/update an SSN). The VIS will query the unblinded staff for subject information and confirm these data prior to determining the subject's treatment group assignment. A copy of the appropriately executed consent and HIPAA authorization documents must be on file at the Hines CSPCC within 24 hours of randomization. If the VIS is not working during normal business hours, the research coordinator can telephone the Hines CSPCC staff to randomize a patient. The subjects or Site Investigators will not be blinded to the study treatment assignment; however all follow-up visits and endpoint adjudications will be performed by a dedicated study nurse blinded to treatment allocation. Patients will be cautioned not to reveal his/her treatment allocation to the blinded study nurse. This blinding precaution will be emphasized by the

procedures written into the study Operations Manual and the communications to the Site Investigator, the Site Coordinator and other study personnel during the kick-off meeting and the teleconference calls throughout the study. Patients will be screened and consented before PCI, but will have the opportunity, after PCI, to decline participation in the study and will not be randomized if they choose not to participate.

4(d) Intervention and Treatment

The randomized treatment regimens of this study include:

- (i) ILLT
- (ii) SMT

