- (2). The EPC-CFU/ml of peripheral blood assessed at various time points (pre-PCI, post-PCI, 30 days of follow-up, and 90 days of follow-up) will be analyzed via Mixed Linear models with random intercepts. The treatment effect, time effect and their interaction will be considered with or without

adjusting for age, pre-existing CAD, pre-existing diabetes, baseline LDL levels, and other relevant covariates such as ACS, peripheral vascular disease, and chronic kidney disease. The statistical test of interest is the time by treatment interaction.

- (3). Contrasts will be used in the Mixed Linear models to compare the differences among any specifically interested time points.

4(g)(vi). Statistical Analysis of Safety Endpoints and Complications: The primary safety endpoints, the secondary safety endpoints, and the incidence of major adverse cardiovascular endpoints (MACE) including death, myocardial infarction, coronary revascularization, and stroke will be analyzed in two ways. For each type of event, the percentage of people who experience the event at least once will be compared using the chi-square test. Logistic regression models will be performed to adjust for the covariates such as age, pre-existing CAD, and pre-existing diabetes. In addition, a similar analysis will be done for all AE and SAE that are possibly or probably attributable to the study intervention.

An event-based analysis will also be done since adverse events can be recurrent. In this analysis, a non-parametric method called the mean cumulative function (MCF)^{35,36} will be used as an alternative to the above crude incidence rate analyses. The overall safety profiles as well as the safety profiles in specific subgroups over the whole study period will be compared for the two randomization groups including the times of event recurrence and censoring mechanisms.

Time to event (survival analysis) will also compare the time to first MACE between treatment groups. A second survival analysis will be performed to identify risk predictors and to evaluate whether the observed treatment effect is modified by adjusting for covariates such as pre-existing CAD and pre-existing diabetes.

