## **Primary Safety Outcome Measure**

The primary safety outcome measures will be the total number of and percentage of patients with major peri-PCI procedure adverse events, such as hypotension, angina, myocardial ischemia, myocardial infarction (if the patient is determined to have had unstable angina rather than non-ST-elevation MI at admission), cerebrovascular event (CVA), vermicular tachycardia, bleeding (at the PCI access and apheresis cannulation sites in the apheresis patients and at the PCI access site in the non-apheresis control patients), and death. The peri-PCI procedure is defined as encompassing the time of the PCI procedure and the time of the subsequent LDL-apheresis procedure for ILLT group versus the time of the PCI procedure for SMT group. All LDL-apheresis-related adverse events in the ILLT group, including any minor expected events, will be recorded.

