## **Analysis of Safety Outcomes**

The primary safety endpoint and the secondary safety endpoints will be analyzed in two ways. For each type of event, the percentage of people who experience the event at least once will be compared using the chi-square test. Logistic regression models will be performed to adjust for the covariates such as age, pre-existing CAD and pre-existing diabetes. In addition, a similar analysis will be done for all AE and SAE that are possibly or probably attributable to the study intervention. An event-based analysis will also be done since adverse events can be recurrent. In this analysis, a non-parametric method called the mean cumulative function (MCF) will be used as an alternative to the above crude incidence rate analyses. The overall safety profiles as well as the safety profiles in specific subgroups will be compared for the two randomization groups including the times of event recurrence and censoring mechanisms.

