## **Analysis of Secondary Effectiveness Outcomes**

The intent-to-treat principle will also be applied to all the secondary effectiveness outcomes analyses.

The change of %NC component of atheroma from baseline to 90-day follow-up will be analyzed using the two-sample t-test. The change scores for those who miss the 90-day follow-up assessment will be set to zero. Analysis of Covariance (ANCOVA) will be performed to evaluate the treatment effect on primary effectiveness outcome adjusting for age, pre-existing CAD, pre-existing diabetes, and baseline LDL levels.

The EPC-CFU/ml of peripheral blood assessed at 4 time points (pre-PCI, post-PCI, 30-day follow-up, and 90-day follow-up) will be analyzed via Mixed Linear models with random intercepts. The treatment effect, time effect and their interaction will be considered with or without adjusting for age, pre-existing CAD, pre-existing diabetes, baseline LDL levels, and other relevant covariates such as ACS, peripheral vascular disease, and chronic kidney disease. The statistical test of interest is the time by treatment interaction. Contrasts will be used in the Mixed Linear models to compare the differences among any specifically interested time points.

The incidence of major adverse cardiovascular endpoints (MACE) including death, myocardial infarction, coronary revascularization, and stroke will be analyzed in two ways. The percentage of people who experience the event at least once will be compared using the chi-square test. Logistic regression models will be performed to adjust for the covariates such as age, pre-existing CAD and pre-existing diabetes. An event-based analysis will also be done since MACE can be recurrent. In this analysis, a non-parametric method called the mean cumulative function (MCF) will be used as an alternative to the above crude incidence rate analyses. The overall safety profiles as well as the safety profiles in specific subgroups over the whole study period will be compared for the two randomization groups including the times of event recurrence and censoring mechanisms. Time to event (survival analysis) will also compare the time to first MACE between treatment groups. A second survival analysis will be performed to identify risk predictors and to evaluate whether the observed treatment effect is modified by adjusting for covariates such as pre-existing CAD and pre-existing diabetes.

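### The primary safety endpoint gives the SMT arm no observation time after randomisation, so its planned between-arm test cannot separate apheresis-caused events from background early post-PCI events

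*Protocol*

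**What the plan says.** Protocol 4(b) makes the primary safety outcome the number and percentage of patients with major peri-PCI events. It lists eight types: hypotension, angina, ischaemia, MI, cerebrovascular event, tachycardia, bleeding and death. The time counted is PCI for everyone, plus "the time of the subsequent LDL-apheresis procedure for ILLT group vs. the time of the PCI procedure for SMT group". The SAP (Primary Safety Outcome Measure) has the same rule: "the time of the subsequent LDL-apheresis procedure for ILLT group versus the time of the PCI procedure for SMT group". Bleeding counts at the PCI access site in both arms, and at the cannulation sites in apheresis patients only.

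On timing, Protocol 4(c)(v) states: "Eligible patients will be randomized to one of two treatment groups (ILLT or SMT) following an uncomplicated index PCI". Exclusion criteria 11 to 18 in 4(c)(iii) remove most patients with serious events around PCI, for example "Pre-PCI, intra-PCI, or post-PCI hemodynamic instability with hypotension".

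On analysis, Protocol 4(g)(vi) says: "For each type of event, the percentage of people who experience the event at least once will be compared using the chi-square test". Logistic regression and mean cumulative functions follow, and the SAP (Analysis of Safety Outcomes) matches.

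On purpose, 4(a) aims to gather further safety data, 1(b) hypothesises that these events will not be a safety concern, and 1(c) asks whether ILLT affects them.

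**The concern.** A randomised safety comparison needs both arms observed over the same time after allocation. Here the SMT window closes before allocation. PCI-time events have the same expectation in both arms and are largely screened out. What remains of the expected difference is the ILLT event rate during the apheresis session, set against nothing.

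Hypotension, angina or access-site bleeding can occur in the hours after PCI without apheresis. In ILLT such an event counts if it falls in the session; in SMT the same event at the same hour does not. Bleeding adds a second asymmetry: inclusion criterion 5 requires two large-bore cannulas in every patient, yet cannulation-site bleeding counts only in ILLT.

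At stake is the reading of the trial's primary safety result. An ILLT excess is expected even if apheresis is harmless, so a reader could not tell whether an observed excess came from the device or from the hours after PCI.

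**Working it through.** **Inputs.** 64 per arm (Protocol section 4); two-sided 0.05 (4(g)(ix)); uncorrected chi-square by event type (4(g)(vi)); eight listed types (4(b)); session of 2 to 4 hours (4(d)(i)). The plan gives no rate, margin or power for this endpoint, so there is no safety figure to reproduce. The arm size does reproduce from the effectiveness calculation: d = 0.65 at 90% power needs 51 per arm, and 102/0.8 = 127.5, rounded up to 128.

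**What the contrast estimates.** Let q be the PCI-time event probability, r the background probability during the ILLT-only time, and a the probability added by apheresis.

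- Written windows: ILLT = 1 − (1 − q)(1 − r − a); SMT = q; difference = (1 − q)(r + a).
- Common window after randomisation: ILLT = r + a; SMT = r; difference = a.

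The written windows identify only the sum r + a, never a alone. This conclusion needs no assumed rate.

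**When a type becomes significant.** For 4 v 0, chi-square = 128 × (4 × 64)² / (64 × 64 × 4 × 124) = 4.13, p = 0.042 (Fisher 0.119). For 3 v 0, p = 0.080. With no SMT events, a type is significant at 4 or more. Fisher's test needs 6 v 0 (p = 0.028).

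**Size under harmless apheresis (a = 0).** r is an assumption. Protocol 2(a)(vii) gives under 1% of treatments for hypotension with apheresis running, which is another population and one component, so 3% and 5% are stress cases. With half the events in one type and q = 0, the false-signal chance is 1 − (1 − P(X ≥ 4 | 64, r/2)) × (1 − P(X ≥ 4 | 64, r/14))⁷. At r = 2% the first tail is 0.0039 and the other seven add almost nothing, giving 0.0040. A multinomial simulation of 400,000 draws agrees (0.0041).

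| Background r | 1% | 2% | 3% | 5% |
|---|---|---|---|---|
| Expected spurious ILLT excess, 64r (patients) | 0.64 | 1.28 | 1.92 | 3.20 |
| At least one such event, 1 − (1 − r)⁶⁴ | 47% | 73% | 86% | 96% |
| False signal by type, even spread, q = 0 | 0.001% | 0.02% | 0.08% | 0.6% |
| False signal by type, half in one type, q = 0 | 0.03% | 0.4% | 1.6% | 7.7% |
| Same, equal windows in both arms | 0.02% | 0.2% | 0.6% | 1.6% |
| Half in one type, q = 2% | 0.8% | 2.1% | 4.0% | 10.0% |
| Composite of all types (not specified), q = 0 | 0.4% | 3.9% | 12.6% | 39.9% |

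With half in one type and q = 0, the chance passes 5% only above r of about 4.3%.

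**Precision of a common-window comparison.** Fisher power at 64 per arm is about 11% for 7% v 2%, and 47% for 12% v 2%.

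**The case against.** The strongest reply is that little rests on this test. The safety objective is data collection, and no margin, power or stopping rule is attached. The ILLT-only time may be only 2 to 4 hours in patients screened for stability. The asymmetry runs against ILLT, so it does not hide harm that occurs in the session. Counting the events of an added procedure is a fair description of its burden. All of this stands, and it keeps the point modest.

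Other safeguards also matter. The SAP plans that "Time to event (survival analysis) will also compare the time to first MACE between treatment groups". It also plans that "a similar analysis will be done for all AE and SAE that are possibly or probably attributable to the study intervention". Under Protocol 4(g)(vi), "safety profiles in specific subgroups over the whole study period will be compared for the two randomization groups". A mean cumulative function is a curve over time, so its early part can be read. Site investigators are unblinded, but 4(c)(v)(2) assigns follow-up visits and endpoint adjudication to a blinded nurse, and 4(f)(iv) sets up a Clinical Events Committee independent of the Study Chair and sites (its blinding is not stated). These lessen the consequence. None specifies a like-for-like early comparison of the listed events: MACE omits hypotension, angina and bleeding, no early contrast is named for the cumulative functions, and adjudication does not change the window.

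Two stronger readings are tempting and unsupported. First, the one hypotension in 20 phase 1 apheresis patients (Protocol 3(c)), attributed to micturition, might seem to demonstrate the fault. Its timing is not given, so it does not; 1/20 also has an exact 95% interval of 0.1% to 24.9%. Second, a reader might infer that a false harm finding is likely. The 12.6% and 39.9% figures need a composite test, which neither document specifies, and stress-case rates.

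**Conclusion.** The point holds as a design fault in the primary safety comparison. Both documents define unequal windows, the SMT window lies wholly before randomisation, and inferential tests are still planned across them. The SAP itself lists index PCI complications among baseline characteristics, although PCI-time events are all that SMT can contribute to this endpoint.

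The practical size is small. At assumed background rates of 1% to 2%, a false signal by event type occurs at most about 0.4% of the time without PCI-time events, and about 2% with them at 2%. These figures assume 64 per arm, harmless apheresis and the stated split across types. The true background rate cannot be fixed from the documents. The structural conclusion depends on none of these assumptions. The effectiveness analysis is unaffected, and the ILLT counts remain useful as description. The point should be fixed because the primary safety contrast cannot answer the question in 1(c), and the data for a valid one are already being collected.

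**What to change.** Amend Protocol 4(b) and 4(g)(vi) and the matching SAP sections.

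1. Make the peri-procedural count descriptive: PCI-time events by arm as pre-randomisation data, and apheresis-session and cannulation-site events as an ILLT summary.
2. Base the between-arm comparison on the same event and bleeding-site definitions in both arms, over one common window from randomisation to a fixed time past the latest apheresis session. The sponsor sets the length.
3. Use the adverse-event data that 4(f)(iv) already collects from consent in both arms, with onset date and time recorded.
4. Give the risk difference with an exact confidence interval as the main output. If a test is kept, Fisher's exact test suits the small counts.

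The cost is text changes and, if not already captured, onset date and time on the form. No extra patient contact is needed.

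The downsides should be stated with the result. Precision is low (power about 11% for 7% v 2%). Protocol 4(e) allows for SMT discharge before 24 hours, so minor SMT events may be missed after discharge. Treatment is open-label and ILLT patients are watched closely during apheresis, so minor events may be detected more readily in ILLT even over a common window.
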